10.4.5 Electrocardiogram (ECG)

A standard 12-lead electrocardiogram (ECG) recording will be performed according to local practice at Screening for identification of any heart failure. An overall interpretation of the ECG as "Normal" or "Abnormal" will be done. If an abnormal finding is considered clinical significant the patient will not qualify for participation in the study.

10.4.6 Serology

Blood samples for HIV, HBV and HCV will be collected and analyzed at Screening. Presence of any of these infections is an exclusion criterion.

The analyses will be performed by local laboratories. Sampling methods and procedures will be in accordance with local routine care. The Blood samples should be labelled with the patient's unique screening number.

10.4.7 Human Leukocyte Antigen (HLA)-typing

Blood samples will be taken at Screening for evaluating the patient's HLA type. HLA-A, HLA-B and HLA-DRB1 will be analyzed centrally by high resolution tissue typing assays at [REDACTED].

The blood samples collected should be labelled with the patient's unique screening number.

The study specific Laboratory Manual, which will be provided to all sites participating in this study, will include full details on blood sample collection, processing, storage, and shipping requirements. All samples will be destroyed after analyses have been performed.

10.5 Safety Assessments

10.5.1 Safety Variables

The following safety variables will be measured:

- AEs
- Physical Examination
- Vital Signs
- Laboratory Safety Assessments blood (hematology, clinical chemistry, and coagulation) and urine including pregnancy
- Other Safety Measurements (auto- and alloimmunization)

10.5.2 Adverse Events

AEs will be recorded during the study period from Screening Visit to the completion of the End-of-Study Visit.

SAEs will be recorded during the study period from Screening Visit to the completion of the End-of-Study Visit or up to 30 days after last dose of IMP administered in the study, whichever occurs later.

AEs will be coded using the Medical Dictionary for Regulatory Activities (MedDRA) version 17.1. The severity of AEs will be graded using the NCI CTCAE version 4.0 [2]. For further information of definitions and reporting of AEs and SAEs, see *Section 11* below.

Medical conditions or diseases present before Screening Visit are only considered AEs if they worsen after Screening Visit. Non-serious events occurring after signing the Informed Consent Form (ICF) but before any assessments made at the Screening Visit are recorded as Medical History in the eCRF.

10.5.3 Physical Examination

The timings of physical examinations are described in *Section 7.2.1* and *Table 2*. A physical examination in accordance with this protocol includes:

Skin, eye, ear, nose and throat, respiratory, cardiovascular, abdomen, lymphatic, and neurological/musculoskeletal (including reflexes)

The outcome of the assessments will be recorded as “normal” or “abnormal”. Abnormal findings will be assessed as “clinically significant” or “not clinically significant”.

Clinically significant findings at Screening will be documented as Medical History. Clinically significant findings after Screening will be documented as AEs, *Section 10.5.2*.

10.5.4 Vital Signs

Vital signs will be monitored throughout the study as safety variables at the time points described in *Section 7.2.1* and in *Table 2*. In connection with vaccination and the 4-hour post-vaccination observation period, a detailed monitoring schedule applies, *Table 3*. The following assessments will be done and should be documented in the vital sign section of the eCRF:

- Supine systolic and diastolic blood pressure (mmHg), after 5 minutes lying down
- Supine heart rate (beats per minute), after 5 minutes lying down
- Body temperature (°C) (according to local practice)
- Height (cm), will be measured only at Screening Visit
- Weight (kg), will be measured at all visits except for Vacc1 and Vacc2 Visits

10.5.5 Laboratory Safety Assessments (Blood and Urine)

Blood and urine samples collected should be labelled with the patient's unique screening number at all study visits. The study specific Laboratory Manual, which will be provided to all sites participating in this study, will include full details on blood sample collection, processing, storage, and shipping requirements (as applicable). All samples will be destroyed after analyses have been performed.

BLOOD

The centrally performed hematology and clinical chemistry analyses will be performed on serum samples by [REDACTED]

The coagulation (PT-INR and APTT) and pregnancy analyses will be performed by local laboratories in accordance with local routine.

In addition to the central analysis of Hb, WBC and platelets, local analysis will be made prior to the vaccinations. Following hospital practice locally analyzed results of Hb, WBC, platelets and clinical chemistry might be needed prior to Nephrectomy unless results from central analyses within 14 days prior to Nephrectomy are available and acceptable. Sampling methods and procedures will be in accordance with local routine for these analyses.

The timing of these assessments is described in *Section 7.2.1*, *Section 7.2.2*, and *Table 2*. At Vaccination Visits, blood samples will be collected prior to vaccination in connection with admission. If needed, for logistical reasons, these samples may be taken the day before vaccination. Also at Nephrectomy blood samples may be taken the day before for logistic reasons.

At least Hb, WBC, platelets, and coagulation status need to be available before vaccination and at least Hb, WBC, and clinical chemistry need to be available before nephrectomy. Analysis of coagulation status at Nephrectomy is not necessary provided the patient is not being treated with anticoagulants. For patients on anticoagulants local sampling practice applies.

The following laboratory safety parameters will be measured in blood, *Table 7*:

Table 7 Laboratory Safety Parameters (Blood)

Category	Laboratory Parameter
Hematology (central analysis and additional local analysis of Hb, WBC and platelets at Nephrectomy and Vaccination Visits)	Hemoglobin (Hb), Red Blood Cells (RBC), White blood cells (WBC), Platelets, Neutrophils, Eosinophils, Basophils, Lymphocytes, and Monocytes
Clinical Chemistry (central analysis)	C-Reactive Protein (CRP), Sodium (Na), Potassium (K), Creatinine ^a , Albumin, corrected Calcium (Ca), Bilirubin, Lactate Dehydrogenase (LDH), Alkaline Phosphatase (ALP), Alanine Transaminase (ALT), Gamma-Glutamyl Transferase (GGT), Aspartate Transaminase (ASAT), GFR based on Creatinine ^b , Gluc ^b , TSH ^b , and Thyroxine (free T4) ^b
Coagulation (local analysis)	PT-INR ^c and APTT ^c
Pregnancy (local analysis)	human Chorionic Gonadotropin (hCG) ^d

- a Locally analyzed creatinine for patients included in the study before 28 August 2017 (if performed as part of clinical routine) to be recorded in the eCRF for Nephrectomy visit
- b To be analyzed at Screening, Sun-Start Visit and at all following visits until end of study
- c To be analyzed at Screening, Nephrectomy and Vaccination Visits
- d To be analyzed in blood at Screening and in either blood or urine at vaccination visits, *Table 8*

The observed values for all categories except pregnancy will be recorded and assessed as “normal” or “abnormal”. Abnormal findings will be assessed as “clinically significant” or “not clinically significant”.

Pregnancy testing in blood will be done to females of childbearing potential at Screening for patients randomized to Intuvax. At Vaccination Visits the pregnancy testing can be done either in blood or urine. The results will be recorded as “Negative” or “Positive”. A patient with a positive test at Screening should not be included in the study. A patient with a positive test at either of the Vaccination Visits should be withdrawn from further study treatment, *Section 11.7*.

URINE

The laboratory safety urinalyses will be performed centrally [REDACTED].

The timing of these assessments is described in *Section 7.2.1* and *Table 2*. At Vaccination Visits, urine samples will be collected prior to vaccination in connection with admission. If needed, for logistical reasons, these samples may be taken the day before vaccination.

The following laboratory safety parameters will be measured in urine, *Table 8*:

Table 8 Laboratory Safety Parameters (Urine)

Category	Laboratory Parameter
Urinalysis (central analysis)	U-Microalbumin, U-Red blood cells, U-Glucose, and U-Nitrite

Pregnancy (local analysis)	Pregnancy dipstick ^a
----------------------------	---------------------------------

a To be analyzed in either blood or urine at Vaccination Visits and in blood at Screening

Unless pregnancy testing at Vaccination Visits is done in blood, urine analysis using dipsticks will be done to females of childbearing potential at Vaccination Visits for patients randomized to Intuvax. The results will be recorded as “Negative” or “Positive” and need to be available before vaccination. A patient with a positive test at either of the Vaccination Visits should be withdrawn from further study treatment, *Section 11.7*.

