7.2.1.4 Nephrectomy Visit

This visit is applicable for all patients.

TIME WINDOWS:

At least 3 days after Vacc2 Visit and within 63 days from Screening Visit for patients randomized to Intuvax followed by sunitinib.

Within 63 days from Screening Visit for patients randomized to sunitinib only.

ACTIVITIES AND ASSESSMENTS:

Prior to Nephrectomy (may be done the day before vaccination for logistical reasons)

- Concomitant Medication, *Section 10.4.4*
- Laboratory Safety Blood Assessments: All patients: Hematology and Clinical Chemistry, for patients on anticoagulants: also PT-INR, and APTT, *Section 10.5.5*

- Laboratory Safety Urine Assessments, *Section 10.5.5*
- █████, *Section 10.2.3.2*
- AEs, *Section 11.2*

Nephrectomy and post Nephrectomy assessments

- Nephrectomy, *Section 9.1.1*
- Biopsies for central assessments of infiltrating CD8+ T-cells and immunohistology, *Section 10.2.2.4* and *Section 10.2.3.3*.
- AEs, *Section 11.2*
- Confirmation of mRCC diagnosis, *Section 10.4.2*

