7.2.1.5 Sun-Start Visit

This visit is applicable for all patients.

TIME WINDOW:

Five (5) to eight (8) weeks after Nephrectomy Visit

NB: The CT scan does not have to be done the very same day as the study visit. However, it has to be done within the above specified time window.

The laboratory safety blood and urine assessments do not have to be done the very same day as the study visit. However, it has to be done a maximum of 3 days prior to the visit.

ACTIVITIES AND ASSESSMENTS:

- CT Scan, *Section 10.4.3* including specification of target lesions *Section 10.2.2.2*
- Concomitant Medication, *Section 10.4.4*
- Physical Examination, *Section 10.5.3*
- Vital Signs, *Section 10.5.4*
- Laboratory Safety Blood Assessments: Hematology and Clinical Chemistry including GFR based on Creat, Gluc, TSH, and Thyroxine [free T4], *Section 10.5.5*
- Laboratory Safety Urine Assessments, *Section 10.5.5*
- Auto- and alloimmunization (only for patients treated with Intuvax), *Section 10.5.6.1* and *Section 10.5.6.2*
- ECOG performance status, *Section 10.2.3.1*
- █████ *Section 10.2.3.2*
- Start of sunitinib treatment. Dispense of sunitinib, *Section 9.1.4*
- AEs, *Section 11.2*

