7.2.1.6 SFU[6W], SFU[12W], SFU[24W], SFU[36W], SFU[48W], and SFU[60W]

These visits are applicable for all patients unless locally CT-verified PD occurs. In case of PD this visit should be considered the End-of-Study Visit.

If SFU[60W] is scheduled ≥ 76 weeks since Screening this visit should be considered the End-of-Study Visit, *Section 7.2.1.7*.

TIME WINDOWS:

SFU[6W]: 6 weeks (± 7 days) after Sun-Start Visit
SFU[12W]: 12 weeks (± 7 days) after Sun-Start Visit
SFU[24W]: 24 weeks (± 7 days) after Sun-Start Visit
SFU[36W]: 36 weeks (± 7 days) after Sun-Start Visit
SFU[48W]: 48 weeks (± 7 days) after Sun-Start Visit
SFU[60W]: 60 weeks (± 7 days) after Sun-Start Visit

NB: The CT/MRI scans do not have to be done the very same day as the corresponding study visits. However, each CT/MRI scan has to be done within the specified time window for the corresponding visit.

ACTIVITIES AND ASSESSMENTS:

The same activities and assessments will be done at these visits as was done on Sun-Start Visit except for auto- and alloimmunization, *Section 7.2.1.5*. In addition to dispense of sunitinib, the site personnel will collect unused and empty sunitinib packages (distributed at the previous visit) from the patient for drug accountability, *Section 9.1.4*.

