7.2.1.7 End of Study Visit

This visit is applicable for all patients.

TIME WINDOW:

78 ± 2 weeks after Screening

NB: The CT/MRI scan does not have to be done the very same day as the study visit. However, it has to be done within the above specified time window.

ACTIVITIES AND ASSESSMENTS:

The same activities and assessments will be done at this visit as was done on SFU[6W] to SFU[60W] Visits, *Section 7.2.1.6*. No dispense of sunitinib will be done.

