AEs	X	X ^c	X ^c	X	X	X	X	X ^k	X ^v	X
Diagnosis Confirmation ^f				X						

a Assessment to be completed before nephrectomy and may be done the day before nephrectomy for logistical reasons

Locally analyzed Creatinine for patients included in the study before 28 August 2017 (if performed as part of clinical routine) to be recorded in eCRF

b Height only at Screening. Weight at all visits except for Vacc1 and Vacc2 Visits.

c See specific flow chart, *Table 3*, for detailed instructions on pre- and post-vaccination assessments.

d Physical examination, ECOG performance, and samples for safety lab and urinalyses may be taken the day before vaccination for logistical reasons

Locally analyzed results for Hb, WBC, platelets, PT-INR, and APTT need to be available before vaccination

Locally analyzed results for Hb, WBC, and clinical chemistry might need to be available prior to nephrectomy

- Analysis of coagulation status at Nephrectomy is not necessary provided the patient is not on anticoagulant treatment. For patients on anticoagulants local sampling practice applies.
- e Pregnancy test in blood at Screening, and in either blood or urine at Vacc1 and Vacc2 Visits. The pregnancy test result is needed prior to each vaccination.
 - f Samples for auto- and alloimmunization analyses will be collected prior to vaccination at Vacc1 Visit. Sampling at Sun-Start Visit only applicable for patients randomized to Intuvax.
 - g To be done when the results from all assessments made are available. Telephone contact with patient to inform about treatment and timing of next study visit.
 - h The prescribed dose to be in accordance with the SmPC/USPI including any dose adjustments.
 - i Return of sunitinib not applicable at Sun-Start Visit and Distribution not applicable at End-of-Study Visit. Standard of Care applies after End-of-Study.
 - j Start of sunitinib administration will be dependent on wound healing. The time window for initiation is five (5) to eight (8) weeks after Nephrectomy.
 - k Post-study collection of survival data.
 - l If CT cannot be used for some reason, MRI is acceptable. The same modality has to be used at all visits.

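### No repeat pregnancy test is scheduled at the start of sunitinib or during it; a control-arm woman's only test can be 119 days before her first dose

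*Protocol*

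**What the plan says.** Three places in the protocol fix the test schedule, and they agree. Table 7 footnote d (10.5.5) reads "To be analyzed in blood at Screening and in either blood or urine at vaccination visits". Table 2 footnote e (7.2.2) reads "Pregnancy test in blood at Screening, and in either blood or urine at Vacc1 and Vacc2 Visits". Table 8 footnote a repeats the same timing for the urine dipstick. The SAP flow chart carries the same schedule. Vacc1 and Vacc2 apply only to patients randomized to Intuvax (7.2.1.2, 7.2.1.3).

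At Sun-Start, 7.2.1.5 lists hematology, clinical chemistry with GFR, glucose and thyroid tests, and urinalysis, followed by "Start of sunitinib treatment. Dispense of sunitinib". It lists no pregnancy test. For the SFU visits, 7.2.1.6 says "The same activities and assessments will be done at these visits as was done on Sun-Start Visit except for auto- and alloimmunization". For End-of-Study, 7.2.1.7 says "The same activities and assessments will be done at this visit as was done on SFU[6W] to SFU[60W] Visits". The gap at Sun-Start therefore carries through to the end of treatment.

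Inclusion criterion 9 (8.2) requires a negative blood test at Screening for every woman of childbearing potential and, for women randomized to Intuvax, a negative test within one day before each dose. Section 11.7 requires contraception until sunitinib is completed (or 90 days after the last Intuvax dose, if later), asks patients to report a pregnancy at once, and takes pregnant patients off study treatment.

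**The concern.** The protocol treats pregnancy on sunitinib as a risk worth managing: contraception runs to the end of sunitinib and pregnancy stops study treatment. Around Intuvax it imposes the same contraception and still checks before each dose. Before sunitinib it does not check again, although sunitinib is listed as an investigational product, is dispensed at study visits and is planned to continue until End-of-Study (9.3).

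A woman who conceives after her last scheduled test (Screening in the control arm, Vacc2 in the Intuvax arm) could start and continue sunitinib with nothing in the visit schedule to reveal it. The stopping rule in 11.7 would then work only if she noticed and reported the pregnancy. What is at stake is avoidable harm to an individual patient, not the trial's comparison of the arms.

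**Working it through.** The plan states no interval between the last pregnancy test and the first sunitinib dose, so there is no figure to reproduce. The interval follows from the visit windows.

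**Inputs**
- Vacc1: Day 2 to 28 (Table 2). Vacc2: 14 ± 3 days after Vacc1 (7.2.1.3).
- Nephrectomy, control arm: "Within 63 days from Screening Visit for patients randomized to sunitinib only" (7.2.1.4). Intuvax arm: at least 3 days after Vacc2, with the same 63-day limit.
- Sun-Start: "Five (5) to eight (8) weeks after Nephrectomy Visit" (7.2.1.5), that is 35 to 56 days.
- Vaccination-visit tests may be done the day before (7.2.1.2).

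**Check of the day count against Table 2.** Vacc2 = 2 + 14 to 28 + 14 = Day 16 to 42; earliest nephrectomy = 16 + 3 = Day 19. Both match.

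**Control arm, Screening test to first sunitinib dose**
- Maximum: 63 + 56 = 119 days (17 weeks), or 118 if Screening counts as Day 1 and nephrectomy falls on Day 63.
- Minimum: none is stated for nephrectomy. Assuming surgery the day after Screening, 1 + 35 = 36 days.

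**Intuvax arm, Vacc2 test to first sunitinib dose**
- Minimum: 3 + 35 = 38 days.
- Maximum on Table 2's nominal days: 63 - 16 + 56 = 103, or 104 if tested the day before Vacc2.
- Maximum using the -3 day window (Vacc2 on Day 2 + 11 = Day 13): 63 - 13 + 56 = 106, or 107 if tested the day before.

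**Comparison.** The limit before an Intuvax dose is 1 day.

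**Chance of conception in the longest gap.** Criterion 9 asks for contraception with less than 1% failure. Assuming that rate is per year, 119/365 × 1% = 0.33%, so under 0.33% per woman. With a purely assumed 10% per year for imperfect use, 119/365 × 10% = 3.3%. The documents do not give the number of women of childbearing potential.

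**Could a blacked-out item be the test?** One Sun-Start item is redacted, but it points to Section 10.2.3.2, under efficacy assessments. Pregnancy testing sits in 10.5.5, and the pregnancy row of Table 2 is legible.

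**What can still change.** Assume the protocol is version 9.0 of February 2019 (the version on which SAP Section 1 says it is based) and that the last visit falls on 30 September 2019, the end of the planned quarter.
- Latest Screening = 30 September 2019 - 76 weeks = 16 April 2018.
- Latest Sun-Start = 16 April 2018 + 119 days = 13 August 2018.
- SFU[36W] = 22 April 2019 and SFU[48W] = 15 July 2019.
- SFU[60W] falls at week 17 + 60 = 77 and so counts as End-of-Study.
- If the 30-day safety evaluation must also fit into that quarter, these dates move about a month earlier.

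**The case against.** The best case for the plan is that sunitinib is a marketed drug given as standard of care, with dosing and restrictions tied to the SmPC/USPI (8.4, 9.3). Testing before each dose of a novel cell product while leaving a marketed drug to its label could be deliberate. The label is not in the documents, so this can be neither confirmed nor ruled out. It is weakened by the protocol's practice elsewhere: chemistry and thyroid tests during sunitinib are scheduled explicitly, not left to the label.

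The safeguards in 11.7 are real, and Extra Visits allow further tests at the investigator's discretion (7.2.1.9). SFU visits are 12 weeks apart after SFU[12W], so self-report would remain the main safeguard between visits even with added tests. None of this replaces a check before dispensing.

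Four stronger readings are tempting, and the documents do not support them.
- A reader might infer that sunitinib starts with no prior test at all. Criterion 9 requires one at Screening, and the Intuvax arm has two more.
- A reader might take the time from Sun-Start to week 78 as untested exposure. Visits end at locally verified progression and treatment can stop for side effects or other reasons (7.2.1.6, 9.3), so that time is a ceiling, not a range of exposure.
- A reader might say the SAP promises on-treatment pregnancy results that will not exist. SAP 6.3.11 derives changes only at visits where a parameter was assessed, and its flow chart has the same schedule.
- A sentence in Protocol 10.5.5 seems to confine the Screening test to women randomized to Intuvax. Criterion 9 and Table 2 say otherwise, and randomization follows Screening. It is a wording conflict, not evidence that control-arm women go untested.

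**Conclusion.** The point holds as a gap in the safety schedule of both arms: no repeat test at or near the start of sunitinib, and none during it. It is worth correcting on patient-safety grounds, but it is modest in scale. The women concerned are probably few, and under the contraception the protocol requires, conception in the gap is unlikely. No efficacy endpoint or between-arm comparison changes.

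The day counts rest on the current visit windows being kept. They do not describe intermediate-risk patients enrolled before version 4.0, who were to start sunitinib only after confirmed progression (SAP 4.1). The conclusion is about what the protocol schedules; a test in routine care or under the label remains possible. On the dates worked out above, an amendment would come too late for sunitinib starts, and only the on-treatment tests could still help the last enrolled patients.

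**What to change.** For women of childbearing potential in both arms, require a negative blood or urine pregnancy test before sunitinib is dispensed at Sun-Start, within the 3 days already allowed for that visit's laboratory samples, and again at each SFU visit where sunitinib is dispensed. State that a positive result means no dispensing and handling under 11.7. The longest gap before the first dose then falls from 119 days to 3.

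Amend Table 2 (pregnancy row and footnote e), 7.2.1.5, Table 7 footnote d and Table 8 footnote a. The SFU visits inherit the Sun-Start list, so they need no separate entry. End-of-Study inherits it too, but no sunitinib is dispensed there, so the text should exempt that visit. In the same amendment, delete the words that limit the Screening test in 10.5.5 to patients randomized to Intuvax, which conflict with criterion 9.

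The cost is one amendment and at most 1 + 6 = 7 dipstick or hCG tests per woman concerned, at visits that already collect blood and urine.
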